2. INVESTIGATIONAL DEVICE

2.1. Manufacturer

GATT Technologies BV (Nijmegen, the Netherlands) is the legal manufacturer of GATT-Patch.

2.2. GATT-Patch

GATT-Patch (Figure 2-1) is a resorbable hemostatic sealing patch, contained in a sterile blister pack within a pouch, for topical use in internal surgery. It does not require freezing or other special storage requirements. It presents as a blue, soft, flexible, gelatin fiber-based carrier impregnated with an NHS-POx / NU-POx granulate. The dimensions of GATT-Patch are 50x100mm. As GATT-Patch is a homogenously impregnated fibrous material, both sides are active and it is also suited to being torn into smaller pieces for application in irregularly shaped structures and areas that are difficult to access with a larger item.

FIGURE 2-1: GATT-PATCH

GATT-Patch will be applied onto the wound site where the flexible and resorbable gelatin patch via contact activation starts the coagulation cascade, further enhanced by dehydrating the blood to concentrate the blood's solid elements leading to a matrix for platelet aggregation and release of coagulation factors enabling fibrin formation 'trapped' in the gelatin fibers. Once the patch is activated, via the combination of P(EtOx-OH-NHS), P(EtOx-NH2) and gelatin, a POx-hydrogel is formed. This POx-hydrogel has two effects: firstly, to adhere the patch to the tissue and secondly to form a seal across the damaged tissue. Both parts together help to ensure high efficacy hemostasis can be achieved.

GATT-Patch is a Class III Medical Device intended for application by trained physicians as an aid to hemostasis and sealing in internal organs during surgery after standard surgical hemostatic techniques have been applied. The effect is local and primarily mechanical and is not dependent on the coagulation status of the patient. The product is not removed at the end of surgery but is resorbed in 4-6 weeks⁷.

⁷ The resorption time was estimated 4-6 weeks based on initial preclinical testing of prototypes. The outcomes of a recent GLP implantation study on the final design of GATT-Patch shows resorption in <4 weeks.

2.2.1. Regulatory Classification

GATT-Patch is indicated for use as an adjunct to hemostasis and as a surgical sealant in surgery for minimal, mild or moderate bleeding sites. GATT-Patch is intended to be used for management of hemorrhage during surgeries on internal organs. GATT Patch will be totally introduced into the human body and intended to remain there after the procedure. It is fully degradable within 4-6 weeks.

According to classification rule 8 of Annex VIII of the EU MDR 4 April 2017, the device is a long term surgically invasive and implantable device. The device will be wholly absorbed and it will undergo a chemical change in the body.

According to classification rule 18 of Annex VIII of the EU MDR 4 April 2017, the device is manufactured utilizing derivatives of animal origin, which are non-viable or rendered non-viable.

Therefore, according to both classification rules, GATT-Patch is classified as a Class III medical device.

2.2.2. Materials

A listing of the raw materials used in the manufacturing of the final finished P(EtOx-OH-NHS) - P(EtOx-NH2) granulate-based hemostatic patches is provided in Table 1. GATT-Patch is an implant, and all components are in direct contact with the human body.

Device Component	Raw Materials in Component	Supplier	CAS Number
Delumers	P(EtOx-OH-NHS) polymer	PolyVation	NA
Polymers	P(EtOx-NH2) polymer	PolyVation	NA
Blue Colorant FD&C Blue No. 1	FD&C Blue No.1	Spectrum Chem. via VWR	3844-45-9
Granulate	P(EtOx-OH-NHS) and P(EtOx-NH2)	GATT Technologies	NA
Porous Gelatin carrier (porcine origin)	Gelatin	Gelita Medical	9000-70-8

TABLE 1: RAW MATERIALS/CHEMICAL COMPONENTS GATT-PATCH

2.3. Intended populations and indications

2.3.1. Intended indications

GATT-Patch is indicated for use as an adjunct to hemostasis and as a surgical sealant in surgery for minimal, mild or moderate bleeding sites when control of bleeding by standard surgical techniques (such as suture, ligature or cautery) is ineffective or impractical. GATT-Patch is intended to be used for management of hemorrhage during surgeries on internal organs, primarily parenchymatous organs such as liver, spleen or kidney; or in other abdominal surgeries. GATT-Patch is intended to be used by physicians trained in performing specific surgical and minimal invasive procedures.

2.3.2. Intended populations

The hemostatic sealant GATT-Patch will be intended for use in adult, adolescent and pediatric patients.

The final recommendations will depend on pre-clinical and clinical data, as the safety and performance of the device has not been yet established for use in specific populations as children, pregnant or lactating women.

It should not be used in patients with a known hypersensitivity to the component materials, including porcine proteins and brilliant blue (FD&C Blue No. 1).

2.4. Intended purpose in the clinical investigation

This clinical investigation focusses on the application of GATT-Patch in subjects that are candidate for elective open liver surgery.

2.5. Technical and functional features

GATT-Patch will be applied to the bleeding site where the flexible and resorbable gelatin patch starts the coagulation cascade via contact with tissue. This is further enhanced by dehydrating the blood to concentrate the blood's solid elements leading to a matrix for platelet aggregation and the release of coagulation factors enabling fibrin formation 'trapped' in the gelatin fibers. Once the patch is activated, via the combination of P(EtOx-OH-NHS), P(EtOx-NH2) and gelatin, a POx-hydrogel is formed. This POx-hydrogel has two effects: (1) to adhere the patch to the tissue and (2) to form a seal across the damaged tissue. Together, these two effects help ensure highly effective hemostasis can be achieved independent of the patient's coagulation status, and that the tissue surface remains sealed, preventing leakage of fluids. The patch is resorbed within 4-6 weeks as tissue healing occurs.

The following technical and functional features are defined for GATT-Patch:

- GATT-Patch is a highly active, fibrous, flexible, blue-colored gelatin fiber-based patch that is homogeneously impregnated with an NHS-POx/NU-POx granulate for topical use during internal surgery.
- GATT-Patch can be stored at room temperature and can be used straight out of the package without preparation time.
- The results of preclinical tests have demonstrated that hemostasis could be obtained with 30 seconds of application time
- A flexible and pliable patch of 100 x 50mm size that can easily be cut to smaller size
- Active on both sides
- The patch is resorbed within 4-6 weeks as tissue healing occurs as demonstrated by a GLP implantation study

2.6. Medical/Surgical procedures

The severity of bleeding will be scored according to the Surface Bleeding Severity Scale (SBSS) [1].

Select the appropriate size of the patch so that it overlaps the margins of the bleeding surface by at least 1 cm. The patch may be cut to the desired size and shape. Dry gloves and surgical instruments (forceps, scissors) should be used to handle, cut and apply GATT-Patch.

Surgeons may use up to three patches, or multiple (cut) parts of patches, as long as total material used is no more than three full patches in total in the patient. Patch may be applied to or overlap a previously applied patch ("patch on patch"). If hemostasis has not been achieved after using three patches, other hemostatic agents/techniques may be used.

The following method of application is provided in the instructions for use of GATT-Patch (DHF-01-QR-008):

- Put GATT-Patch on a saline wetted gauze or surgical sponge and apply to the bleeding area, with at least 1 cm margins. Hold in place with uniform pressure over the entire patch surface for 30 seconds. Gently remove the wet gauze from the patch. If complete hemostasis has not been achieved in 30 seconds, re-apply pressure with a saline wetted gauze or surgical sponge for an additional 30 seconds;
 - If hemostasis is not complete with a single patch and blood comes through the patch, apply a new (piece of) GATT-Patch on the bleeding site with a 1cm overlap with tissue or previously placed GATT-Patch on all sides ("patch-on-patch"). Apply according to the steps above.
 - If hemostasis is not complete because GATT-Patch is not adherent to the underlying tissue, with or without hematoma formation underneath, remove the non-adherent part and apply a new (piece of) GATT-Patch on the bleeding site with a 1cm overlap with tissue or previously placed GATT-Patch on all sides ("patch-on-patch"). Apply according to the steps above.
 - Repeat the above steps as necessary, with a maximum of 2.1 cm2 / kg of patient body weight, or approximately 3 patches in a normal adult patient, is covered by GATT-Patch and remains in-situ at the end of the operation.
- It is recommended that dry parts of GATT-Patch after application are wetted via a salinesoaked wet gauze or by irrigation.
- When applying GATT-Patch, minimize contact with wet or bloody surgical instruments or gloves as the adhesive may adhere to other surfaces.
- Leave GATT-Patch in situ after hemostasis has been achieved. Do not try to forcefully remove the patch.
- Do not remove GATT-Patch at the end of the surgery. Excess GATT-Patch material may be removed carefully, at the discretion of the surgeon.
- Irrigate GATT-Patch after application and hemostasis, assess potential re-bleedings prior to closing the laparotomy.

It is recommended to use the product within 3 hours after opening (after 3 hours, the performance of the device may decrease). To ensure adequate endpoint assessment in this clinical investigation, no manipulation of GATT-Patch and the Target Bleeding Site should be performed up to 5 minutes after GATT-Patch application, unless extra pressure or an additional patch is required per instructions for use and scenarios below.

As described in the IFU, certain situations can occur in which hemostasis is not achieved after an initial 30 seconds application time. The following description, and Figure 2-2, provide more details:

Hemostasis is achieved (SBSS 0) but blood builds up underneath GATT-Patch as shown by a dome formation (e.g. caused by inadequate pressure) → re-apply 30 seconds of pressure. If after an additional 30 seconds of pressure a dome again arises, cut away the dome and apply a new (piece of) GATT-Patch on the bleeding site with a 1cm overlap with tissue or previously placed GATT-Patch on all sides. Apply pressure for 30 seconds. Repeat as necessary up to 5 minutes. If hemostasis is achieved (SBSS 0) and GATT-Patch is adhesive to the tissue → leave GATT-Patch in place and do not manipulate until 5 minutes from the initial application have passed.

- Hemostasis is not achieved (SBSS ≥1) because GATT-Patch is not adherent to underlying tissue (e.g. caused by inadequate pressure) → re-apply 30 seconds of pressure. If after an additional 30 seconds of pressure (a part of) GATT-Patch is not adherent, cut away the non-adherent part and apply a new (piece of) GATT-Patch on the bleeding site with a 1cm overlap with tissue or previously placed GATT-Patch on all sides. Apply pressure for 30 seconds. Repeat as necessary up to 5 minutes. If hemostasis is achieved (SBSS 0) and GATT-Patch is adhesive to the tissue → leave GATT-Patch in place and do not manipulate until 5 minutes from the initial application have passed.
- Hemostasis is not achieved as blood is coming through GATT-Patch (SBSS ≥1) → re-apply 30 seconds of pressure. If after an additional 30 seconds of pressure blood is still coming through the patch (e.g. potential cause is puncture of the patch), apply an additional (piece of) GATT-Patch on the bleeding site (e.g. "patch-on-patch") with a 1cm overlap on the previously placed GATT-Patch on all sides. Apply pressure for 30 seconds. Repeat as necessary up to 5 minutes. If hemostasis is achieved (SBSS 0) and GATT-Patch is adhesive to the tissue → leave GATT-Patch in place and do not manipulate until 5 minutes from the initial application have passed.

FIGURE 2-2: GATT APPLICATION FLOWCHART

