5.2. Primary endpoint

The primary performance endpoint is defined as non-inferiority of GATT-Patch compared to the standard of care regarding the percentage of cases achieving hemostasis at 3 minutes (i.e., demonstrate GATT-Patch is significantly greater than literature-based performance goal of 65.4%).

Hemostasis will be defined by a grade of 0 (None/Dry) on the Surface Bleeding Severity Score (SBSS). The SBSS provides a validated score for assessment of bleeding at the target site, and consists of 6 subscales (0=none, 1=minimal, 2=mild, 3=moderate, 4=severe; not immediately life-threatening, 5=extreme; immediately life threatening) [1]. Investigators will be trained on the assessment scale prior to the investigation to have consistent assessment of bleeding at the target site (Section 2.7).

Achievement of hemostasis will be verified every 30 seconds, starting from the time that GATT-Patch is positioned and pressure is initiated. If hemostasis has not been achieved after 5 minutes of application (SBSS 1-5), then treatment is considered a failure and additional hemostatic agents or techniques may be used.

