6.4.4. Admission before surgery

The following baseline data will be captured during admission before surgery:

- Confirmation of inclusion/exclusion criteria
- Physical examination
- Relevant concomitant medication
- Laboratory test data

6.4.5. Treatment

GATT-Patch will be used to control bleeding during open liver surgery. Each surgery will be performed according to the standard procedures at the hospital, with exception of the use of GATT-Patch. GATT-Patch will be used if the subject has an appropriate bleeding site (SBSS 1, 2 or 3 and no contraindications). Use of GATT-Patch will only be considered during and/or after resection when control of bleeding by standard surgical techniques (such as suture, ligature or cautery) is ineffective or impractical, and the surgeon has made the decision to apply a topical hemostatic product. If there are multiple appropriate bleeding sites, the first encountered bleeding site that requires topical hemostat application will be considered for the primary endpoint.

The handling instructions for GATT-Patch are provided in the Instructions for Use of the device (DHF-01-QR-008). Select the appropriate size of the patch so that it overlaps the margins of the bleeding surface by at least 1 cm. The patch may be cut to the desired size and shape. Dry gloves and surgical instruments (forceps, scissors) should be used to handle, cut and apply GATT-Patch. GATT-Patch can be placed on a wet gauze prior to placement, and after excess blood is removed from the bleeding site, directly applied on the bleeding site with continuous pressure. Failure is considered if after 5 minutes no hemostasis was obtained. Up to 3 full patches may be used. The patch may be applied to or overlap a previously applied patch ("patch on patch").

Achievement of hemostasis will be verified every 30 seconds. The primary performance endpoint is defined by the percentage of cases achieving hemostasis at 3 minutes. Hemostasis will be defined by a grade of 0 (None/Dry) on the SBSS¹⁰. If hemostasis has not been achieved after 5 minutes of

¹⁰ The Surface Bleeding Severity Score (SBSS) provides a validated score for assessment of bleeding at the target site, and consists of 6 subscales (0=none, 1=minimal, 2=mild, 3=moderate, 4=severe; not immediately life-

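### Protocol 2.6 sets two unreconciled limits: three full patches can exceed the 2.1 cm²/kg cap in subjects under 71.4 kg, and no visible rule opens rescue when the cap is reached

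*Protocol*

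**What the plan says.** **Quantity.** Protocol 2.2 gives the patch size: "The dimensions of GATT-Patch are 50x100mm". Protocol 2.6 first sets a fixed ceiling, under which "total material used is no more than three full patches in total in the patient". Later in 2.6, the application steps taken from the Instructions for Use (IFU) allow repetition "with a maximum of 2.1 cm2 / kg of patient body weight, or approximately 3 patches in a normal adult patient". This second limit applies to patch that covers the site and is still there when the operation ends. Protocol 6.4.5 (Treatment) states only the fixed ceiling: "Up to 3 full patches may be used". The scenarios at the end of 2.6 (dome formation, non-adherence, blood coming through) tell the surgeon to add patch and repeat until 5 minutes, with no mention of the weight cap. The eligibility criteria in 6.3.1 and 6.3.2 set no minimum body weight.

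**What stays in.** Protocol 2.6 says "Do not remove GATT-Patch at the end of the surgery", but its next sentence lets the surgeon carefully take away excess material.

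**Rescue.** Protocol 2.6: "If hemostasis has not been achieved after using three patches, other hemostatic agents/techniques may be used". The same section asks for "no manipulation of GATT-Patch and the Target Bleeding Site should be performed up to 5 minutes after GATT-Patch application, unless extra pressure" or a further patch is needed. Protocol 5.2 sets the switch point "after 5 minutes of application (SBSS 1-5), then treatment is considered a failure and additional hemostatic agents or techniques may be used". Protocol 6.4.5 agrees with 5.2 for the target site. Its own sentence about three patches concerns a different bleeding site.

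**Reporting.** SAP 12.1.6 summarises patches per cm² of bleeding surface. No planned table gives patch area per kg.

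**The concern.** The weight cap is the protocol's stated maximum for a first-in-human resorbable implant. A surgeon working from 6.4.5 or from the 2.6 scenarios sees permission for three patches and an instruction to keep adding, but not the cap. In a lighter subject that can lead to more material being left in place than 2.6 allows.

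A subject can also reach the cap while still bleeding. No visible sentence then says that another hemostat may be used before 5 minutes, because the early permission in 2.6 counts patches rather than cm² per kg. The surgeon may exceed the cap, keep pressing until 5 minutes, or deviate.

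An excess would be hard to see afterwards. The planned summary does not use body weight, and because 6.4.5 permits three patches, a site may not record the excess as a deviation. Safety is half of the success rule in the SAP Summary, so exposure against the protocol's own maximum should be visible.

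**Working it through.** **Inputs.** Patch 5 × 10 cm = 50 cm² (Protocol 2.2). Fixed ceiling of 3 full patches, and cap of 2.1 cm²/kg (both Protocol 2.6). 39 planned treated Stage II subjects (Protocol 7.2). Body weights are not given.

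**1. The protocol's own equivalence.** The protocol equates the cap with about three patches in a normal adult but gives no weight for that adult. Assuming 70 kg: 2.1 × 70 = 147 cm², and 147/50 = 2.94 patches. The equivalence is reproduced when full patch area is counted.

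**2. Break-even weight.** 3 × 50 = 150 cm²; 150/2.1 = 71.4 kg. Above this weight the three-patch ceiling is the tighter limit; below it the cap is. For two patches the break-even is 100/2.1 = 47.6 kg.

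**3. Excess if three full patches lie flat and all stay in place.** Cap = 2.1 × weight. Excess = 150/(2.1 × weight) − 1.

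| Weight (kg) | Cap (cm²) | Cap in patches | 150 cm² as cm²/kg | Excess over cap |
|---|---|---|---|---|
| 50 | 105.0 | 2.10 | 3.00 | 42.9% |
| 55 | 115.5 | 2.31 | 2.73 | 29.9% |
| 60 | 126.0 | 2.52 | 2.50 | 19.0% |
| 65 | 136.5 | 2.73 | 2.31 | 9.9% |
| 70 | 147.0 | 2.94 | 2.14 | 2.0% |
| 80 | 168.0 | 3.36 | 1.88 | none |

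**4. Effect of overlap, if the cap means tissue area covered.**
- Three in a row, 1 cm overlaps on the long edges: (15 − 2) × 10 = 130 cm²; 130/2.1 = 61.9 kg.
- Three in a row, 1 cm overlaps on the short edges: (30 − 2) × 5 = 140 cm²; 140/2.1 = 66.7 kg.
- Three fully stacked: 50 cm²; 50/2.1 = 23.8 kg, so the cap hardly matters.

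If stacked layers each count, 71.4 kg stands unless material is removed. The wording does not say which reading applies.

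**5. How many subjects could be concerned.** For assumed normal weight distributions with mean 70 to 85 kg and SD 12 to 18 kg, the share under 71.4 kg runs from about 13% to 55%. That is 0.129 × 39 ≈ 5 to 0.547 × 39 ≈ 21 subjects. These are subjects below the break-even weight, not subjects over the cap. Only those needing more than about two patches could exceed it.

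**6. Rescue triggers side by side.**

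| Place | When another hemostat may be used |
|---|---|
| 2.6, limit on patches | After three patches, no time condition |
| 2.6, hold on manipulation | Not before 5 minutes; exceptions are pressure or more patch |
| 5.2 | No hemostasis at 5 minutes |
| 6.4.5, target site | No hemostasis at 5 minutes |
| 6.4.5, three patches used | Only for another bleeding site |
| Weight cap reached | No visible sentence |

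**7. Illustration in time.** Each patch takes 30 s plus a further 30 s of pressure; ignore handling time. Two patches are used by 120 s. At 50 kg they are 100 of the 105 cm² allowed by patch area, so little beyond pressure remains for 300 − 120 = 180 s. In a subject above 71.4 kg, three patches are used by 180 s. The patch-count rule in 2.6 then opens rescue 300 − 180 = 120 s before the other rules do.

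**The case against.** The two limits measure different things: one counts material used, the other what covers the site and remains at the end. At a failing site the prescribed method is patch-on-patch or cutting away the loose part, and excess may be removed. A reader might infer that every subject under 71.4 kg given three patches exceeds the cap. The documents do not support that; it is true only of full patches laid flat and all left in place. The conflict still matters, because the fixed ceiling applies to the whole patient, several bleeding sites are foreseen (6.4.5; SAP 12.3.1), and patches at separate sites need not overlap. Removal of excess is left to discretion and not tied to the cap.

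Section 6.4.5 refers to the IFU for handling, and 2.6 presents the cap as part of that IFU's method. Two ceilings can hold together, with the tighter one binding. That is the sensible reading, and it stands. The protocol does not state it where the surgeon is told what to do.

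A reader might take 6.4.5 to key target-site rescue to three patches. It does not; it uses 5 minutes, and only 2.6 uses the patch count. A reader might also infer that rescue is forbidden at the cap. Section 9.2 allows deviation in an emergency to protect the subject, eligible bleeding is limited to SBSS 1 to 3, and continued pressure is allowed throughout. The hold in 2.6 has a stated purpose, endpoint assessment. Figure 2-2 and the full IFU were not seen and may contain the missing step.

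Two further inferences go too far. Toxic response is a listed risk in Protocol 4.2, but nothing visible makes 2.1 cm²/kg a toxicity threshold. Nor do the documents show that early rescue would inflate the primary result, since Protocol 7.1.1 defines success as hemostasis using GATT-Patch.

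**Conclusion.** The concern holds as a gap in the treatment instructions. The protocol states a weight-based maximum once, gives patch permission elsewhere without it, and does not say which limit governs or how layers count. Below 71.4 kg, three full flat patches left in place exceed the cap, by 19% at 60 kg and 43% at 50 kg. These are upper bounds; with 1 cm overlaps the break-even is about 62 to 67 kg. The number of subjects who would exceed the cap is unknown and could be zero, because neither weights nor patches per subject are given.

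The rescue rules disagree on the visible text (three patches without a time condition against 5 minutes), and reaching the cap triggers nothing. This part is less certain because Figure 2-2 and the IFU were not seen.

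Sample size, alpha, power and the primary test are unaffected. This is a minor to moderate safety clarification.

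**What to change.** 1. In Protocol 2.6, its troubleshooting scenarios and 6.4.5, state one limit: the smaller of three full patches and 2.1 cm²/kg left in place. Say whether stacked layers count. Add a short weight table (50 kg: 2.1 patches; 60 kg: 2.5; 71.4 kg or more: 3).
2. In 2.6, 5.2 and 6.4.5, state one target-site rescue trigger in the same words, covering the case where the limit is reached without hemostasis. One workable form is at the limit or at 5 minutes, whichever comes first. Align Figure 2-2 and the IFU if they differ.
3. In SAP 12.1.6, add the cm² left in place per kg and the number of subjects above 2.1. Showing this for the Safety population as well would bring in Stage I, which the FAS and PP leave out.

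The cost is a short protocol clarification and one or two table rows. Weight (SAP 8.1) and number of devices (Protocol 6.4.5) are already collected; area left in place may need one CRF field (the CRF was not seen). The downside is that lighter subjects reach the limit sooner, so a few who might have become dry by 3 minutes with more patch could count as failures. No new failure rule or per-protocol rule is needed for this fix.
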